The fixation provided by the Acutrak headless compression screws provide sufficient fixation to achieve union and a favorable clinical outcome in both horizontal and vertical medial malleolus fractures when compared to bicortical and unicortical screw fixation, tension band wiring, and mini-fragment or buttress plating. However, minimizing the amount of dissection required for implantation as well as lack of prominent hardware surfaces will reduce the incidence and severity of hardware related pain and correspondingly the necessity of hardware removal.

Specific Aims

- 1) *Prospectively establish equivalence with respect to fracture union rate after Acutrak headless compression screw fixation when compared to other fixation methods for medial malleolus fractures.*
- 2) *Prospectively establish equivalence with respect Patient Reported Outcome Measurement Information System (PROMIS) scores after Acutrak headless compression screw fixation when compared to other fixation methods for medial malleolus fractures.*
- 3) *Prospectively establish superiority with respect to hardware related pain after Acutrak headless compression screw fixation when compared to other fixation methods for medial malleolus fractures.*
- 4) *Prospectively establish superiority with respect to the hardware removal rate after Acutrak headless compression screw fixation when compared to other fixation methods for medial malleolus fractures.*

Study Design

Institutional Review Board and HIPAA

The institutional review boards of Stanford Hospital and Clinics and the Kaiser Permanente Hospital, South Sacramento will review and approve this study prior to initiation. All patient information will be kept confidential in accordance with HIPAA and only the study coordinator and the protocol director will have access to the data.

Inclusion/Exclusion Criteria

All ankle fractures that undergo open reduction internal fixation of the medial malleolus in adults at or over 18 years-of-age will be considered for inclusion.

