We will specifically exclude pediatric ankle fractures in children under 18 years-of-age, tibial plafond (pilon) fractures in children and adults, medial malleolar osteotomies to access the talus, perform an ankle fusion, or deal with a pathologic lesion, osteonecrosis, or infection due to their diversity in diagnosis, management, and weight bearing status. Patients with prior surgical treatment of the ankle for fracture, deformity, infection, neoplasia, or other pathologic process on the ipsilateral extremity will also be excluded.

Patients that are non-weight bearing on one or both lower extremities prior to sustaining their ankle injury will be excluded.

Randomization

All elective and emergent admissions to Stanford Hospital and Clinics and Kaiser Permanente – South Sacramento that meet our inclusion/exclusion criteria will be identified and solicited for consent. Patients will be randomized by sealed envelope to surgical fixation with traditional headed screws, plates, and wires or Acutrak headless compression screws. At the time of randomization, the fracture pattern and severity, past medical history and medications, and demographic data will be documented.

Follow-up Protocol

After operative fixation, patients will receive fracture follow-up with a clinical evaluation for tenderness, radiographs to evaluate stability and union at 2 weeks, 6 weeks, 3 months of surgery and complete the PROMIS and VAS pain scores. Patients will be followed by telephonically once the fracture union is confirmed radiologically by the operating surgeon at 6 months, 1 year, and 2 years after surgical fixation. The VAS pain scores will be administered telephonically and the PROMIS questionnaires will be mailed to the patients (Table 1).⁹

Table 1: Protocol Summary

Time and Event Table	Injury/Office	2 weeks	6 weeks	3 months	6 months (over Telephone & mail)	1 year (over Telephone & mail)	2 years (over Telephone & mail)
Discuss Study	X						
Screening Log	X						
Informed Consent	X						
Eligibility Worksheet	X						
Demographic Data	X						
Medical History	X						
Randomization	X						
Clinical Assessment							
•Medial Ankle Tenderness	X	X	X	X	X	X	X
•Lateral Ankle Tenderness	X	X	X	X	X	X	X
Patient Reported Outcomes							
•PROMIS Score	X	X	X	X	X	X	X
•VAS Pain (by location)	X	X	X	X	X	X	X
•On Narcotics (yes/no)	X	X	X	X	X	X	X
Radiographs							
•Anterior-to-Posterior Ankle	X	X	X	X	-	-	-
•Lateral Ankle	X	X	X	X	-	-	-
Operative/Device	X						

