Removal of Hardware		X	X	X	X	X	X
Adverse Event	X	X	X	X	X	X	X
End of Study							X

Criteria for Removal of Hardware

Hardware may be removed if there is a surgical indication or patient/surgeon preference for removal. Patients will be asked whether they feel bothersome sensitivity at the both medial and lateral malleolus. If they mention sensitivity to light touch that is not bothersome they should not be subjected to hardware removal unless by patient or surgeon preference and noted as medial or lateral hardware removed for preference. On the other hand, if they mention bothersome sensitivity, it would be rated on a 0-5 Likert intensity scale. All bothersome sensation will be subjected to hardware removal and noted as removal for sensitivity. Other reasons for hardware removal indications include infection and non-union or mal-union requiring revision open reduction and internal fixation. The location of symptoms and reason for hardware removal should be specified and documented.

Documentation of Fracture Union

Union will be defined as a pain free fracture site on examination with evidence of radiographic healing and a return to full weight bearing confirmed by the operating surgeon

Power Analysis and Statistics

Retrospective review of ankle hardware removal cases indicates that 6% (8/126) of patients have their hardware removed for non-pain issues (e.g., infection, etc.) at 6 months and 17% (22/126) of patients have their hardware removed for pain on the medial or lateral side of the ankle at 6 months.⁸ Hence, the overall rate of hardware removal is 24% but if we can reduce half of the medial hardware removals the overall rate would be 14.5%. To detect this 9.5% difference, it would take 424 randomized patients (alpha = 0.05, and 80% power). Medial hardware removal will be prohibited for lateral hardware pain.

Utilizing the STRIDE database available at Stanford University, there have been 155 procedures involving fixation of the medial malleolus (CPT: 27766, 27814, 27822, 27823) over the past three years. Assuming a similar procedure burden at the other major Level I Trauma center and extrapolating this three-year data, we estimate the capability to enroll 500 patients over three years.

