Number of Subjects	Utilizing the STRIDE database available at Stanford University, there have been 155 procedures involving fixation of the medial malleolus (CPT: 27766, 27814, 27822, 27823) over the past three years. Assuming a similar procedure burden at another major Level I Trauma center at Kaiser Permanente Hospital, South Sacramento and extrapolating this three-year data, we estimate the capability to enroll and randomize over 500 patients requiring medial malleolus fixation over three years between the three centers.
Number of Sites	Three Level I Trauma Centers will participate: 
 • Stanford Hospital and Clinics • Kaiser Permanente – South Sacramento • Brigham and Women's Hospital- Boston
Procedure Schedule	See Table 1
Subject Duration	The estimated duration for each subject is 2 years. Subjects are released from postoperative follow-up after post-operative observation for two years.
Study Duration	The estimated duration of the study is 5 years: 3 years for enrollment and 2 year for postoperative follow-up for each enrolled subject.
Safety	All adverse events and complications will be continuously monitored throughout the study. The type and frequency will be analyzed by a medical monitor.
Statistical Methods	All continuous variables will be reported as the mean and errors are reported as standard deviation. All categorical variables will be reported as the subset number and percentage of the total. Comparisons will be performed with the appropriate statistical test when indicated. Statistical significance will be set at p less than 0.05 with an appropriate Bonferroni correction for multiple comparisons when indicated.

References

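### The union definition has no rule for weight bearing restricted by another injury, so a healed medial malleolus can be recorded as not united

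*Combined protocol and SAP*

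**What the plan says.** **Eligibility.** The Inclusion/Exclusion Criteria section admits "All ankle fractures that undergo open reduction internal fixation of the medial malleolus in adults" from 18 years of age. Its one criterion on the patient's own weight bearing reads "Patients that are non-weight bearing on one or both lower extremities prior to sustaining their ankle injury will be excluded". The Critical Eligibility Criteria row of the Acumed Study Summary repeats it. No criterion concerns another injury from the same event.

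**Source of patients.** The Randomization section draws on "All elective and emergent admissions to Stanford Hospital and Clinics and Kaiser Permanente" (South Sacramento). The Number of Sites row says "Three Level I Trauma Centers will participate". The baseline items listed under Randomization are fracture pattern and severity, history, medications and demographics. Concurrent injury is not named.

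**Union.** Documentation of Fracture Union says "Union will be defined as a pain free fracture site on examination with evidence of radiographic healing and a return to full weight bearing". The surgeon who operated must confirm it. The definition gives no assessment time and no clause on why weight bearing might be restricted.

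**Other wordings.** The Follow-up Protocol moves patients to telephone contact "once the fracture union is confirmed radiologically by the operating surgeon", a radiological criterion only. The Study Objectives row speaks of a union rate that is both radiographic and clinical.

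**Role of union.** Equivalence in union rate is Specific Aim 1 and is listed under both the secondary and the safety objectives. It is not the primary objective.

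**The concern.** Radiographic healing and a pain-free site describe the fracture. Return to full weight bearing describes what the patient is doing, and that can be limited by something other than the ankle. Someone who breaks the medial malleolus and, in the same event, a femur, the pelvis or the other leg is eligible, and may be off full weight for the second injury after the first has healed. Followed literally, the definition denies union to that patient.

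The two union wordings make this harder to correct later. A patient whose radiographs show healing meets the condition for telephone follow-up while still failing the fuller definition. Table 1 schedules no radiographs after 3 months, and its later contacts are by telephone and mail. The definition needs an examination and the surgeon's confirmation, and nothing says how a later return to full weight would change the recorded status. Because concurrent injury is not a named baseline item, the affected patients may not be identifiable at analysis.

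At stake are a union rate that cannot be read as a healing rate, and a less precise equivalence comparison.

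**Working it through.** **The plan's own figure.** Power Analysis and Statistics gives 424 patients to detect hardware removal of 24% against 14.5% (alpha 0.05, 80% power). With p̄ = 0.1925 and a pooled variance under the null:

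n per arm = [1.645·√(2·0.1925·0.8075) + 0.842·√(0.24·0.76 + 0.145·0.855)]² / 0.095² = 212, so 424 in total.

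This matches with one-sided alpha; two-sided alpha gives 270 per arm, 540 in total. The figure has no union input. It is used here only as the source of 212 per arm, assuming 1:1 allocation.

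**Assumptions for union.** The documents give no expected union rate, equivalence margin or share of affected patients. I assume:
- true union of 95% in both arms;
- a share f of patients with healed ankles who are still off full weight because of another injury when union is judged, equal in both arms. This is narrower than the share with any concurrent injury.

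**Formulas.**
- Recorded union: p = 0.95 × (1 − f)
- Half-width of the 95% interval for the difference: 1.96 × √(2p(1 − p)/212)
- Healed ankles recorded as not united, per arm: 212 × 0.95 × f
- Their share of recorded non-unions: 0.95f/(1 − p)
- A true 5-point deficit as recorded: 5 × (1 − f)

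| f | Recorded union | Half-width (points) | Healed but recorded not united, per arm | Share of recorded non-unions | True 5-point deficit appears as |
|---|---|---|---|---|---|
| 0 | 95.0% | 4.1 | 0 | 0 | 5.0 |
| 2% | 93.1% | 4.8 | 4 | 28% | 4.9 |
| 5% | 90.3% | 5.6 | 10 | 49% | 4.75 |
| 10% | 85.5% | 6.7 | 20 | 66% | 4.5 |

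**Does this favor an equivalence conclusion?** I use two one-sided tests at 0.05 with an assumed margin m. D is the recorded deficit and SE its standard error:

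Pr(conclude equivalence) = Φ((m − D)/SE − 1.645) + Φ((m + D)/SE − 1.645) − 1

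True union 90% against 95%, m = 10 points:
- f = 0: D = 0.05, SE = √((0.90·0.10 + 0.95·0.05)/212) = 0.02547, giving 62.5%
- f = 5%: D = 0.0475, SE = √((0.855·0.145 + 0.9025·0.0975)/212) = 0.03162, giving 50.5%
- f = 10%: D = 0.045, SE = √((0.81·0.19 + 0.855·0.145)/212) = 0.03620, giving 44.1%

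No true difference:
- m = 10 points: 99.8% at f = 0, 93% at 5%, 80% at 10%
- m = 5 points: 53%, 7% and 0%

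True deficit equal to a 10-point margin (85% against 95%): 5.0%, 6.7% and 8.3%. Of the cases shown, only this one has the chance of concluding equivalence rising.

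**The case against.** The strongest reply is that the documents never say these patients count as non-unions. That stands. The definition has no deadline, so a patient who reaches full weight later could still meet it; 3 months is the last scheduled radiograph, not a stated endpoint time. The text does not say whether full weight bearing refers to the injured ankle or to the patient as a whole, so an injury to the other leg may not matter, and an arm injury need not. The Follow-up Protocol wording is purely radiological. A reader might infer that every patient with a concurrent limb injury is scored as not united. The text supports only that such a patient can be, if the definition is applied as written.

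A reader might also infer that the pre-injury exclusion exists because union is scored on weight bearing. The protocol gives no reason for that exclusion. The phrase "due to their diversity in diagnosis, management, and weight bearing status" belongs to the preceding exclusions (pediatric and pilon fractures, osteotomies) and does not mention union. It shows only that the authors regarded weight-bearing status as a source of heterogeneity.

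Finally, randomization should balance the problem, and union is not the primary objective. Both are correct. They rule out an expected spurious difference between arms and limit the importance of the point. They do not restore the lost precision or make the recorded rate a healing rate.

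**Conclusion.** The gap is real and moderate in importance. As written, the plan can record a healed medial malleolus as not united because of an unrelated restriction, and it provides no means of finding or reclassifying such patients. With 212 per arm and 95% true union, the half-width grows from 4.1 points to between 4.8 and 6.7 as f goes from 2% to 10%, and recorded union falls to between 93.1% and 85.5%. These figures illustrate a range; f, the union rate and the margins are assumptions.

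A tempting stronger reading is that false non-unions in both arms push the trial toward declaring equivalence. The calculation does not support that as a general statement. A true difference shrinks only slightly (5 points to 4.5 at f = 10%), and the wider interval usually outweighs this: with a true 5-point deficit and a 10-point margin, the chance of concluding equivalence falls. It rises, modestly, when the true deficit equals that margin. The main harm is an understated union rate and lost precision, on a secondary and safety endpoint. The primary objective and the 424 do not depend on it.

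**What to change.** 1. Under Randomization, add a baseline field for any concurrent injury expected to restrict lower-limb weight bearing.
2. In Documentation of Fracture Union, state that for the union endpoint a restriction due to a recorded other injury does not count as non-union, and that union is then judged on the pain-free site and radiographic healing.
3. Report radiographic union alone, for all patients, as a sensitivity analysis.
4. Reconcile the union wording in the Follow-up Protocol, Documentation of Fracture Union and the Study Objectives row.

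The cost is one field, a sentence or two and one extra analysis, with no change to patient care. The small downside is that union rests on fewer components in a minority of patients; the sensitivity analysis shows whether that matters. Extending the exclusion to patients with concurrent injuries is not advised: it would narrow a deliberately broad population and cost recruitment to solve a problem of endpoint definition.

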Static load to failure testing our laboratory has challenged this observation in vertical medial malleolus fracture patterns as well.⁵⁻⁷ We recently demonstrated (manuscript submitted) superior stiffness (463 ± 91 N/mm) and load at 2 mm of ankle joint displacement (922 ± 297 N) with antiglide plate fixation versus unicortical screw fixation (111 ± 35 N/mm and 284 ± 51 N, respectively) and bicortical screw fixation (279 ± 30 N/mm and 429 ± 112 N, respectively) of vertical medial malleolus fractures ($p < 0.05$).

Superior fixation requires extensive dissection and fixation known to result in prominent hardware and hardware related pain. None of these fixation methods address the lack of soft tissue to cover the medial malleolus and the common practice of hardware removal to address post-fixation hardware pain. Retrospective review of ankle hardware removal cases indicates that 6% (8/126) of patients have their hardware removed for non-pain issues (e.g., infection, etc.) at 6 months and 17% (22/126) of patients have their hardware removed for pain on the medial or lateral side of the ankle at 6 months.⁸

The headless configuration of the Acutrak system makes it ideal for medial malleolus fixation and may obviate the need for hardware removal. We recently demonstrated (manuscript submitted) superior stiffness and load at 2 mm of ankle joint displacement of an Acutrak screw construct (244 ± 58 N/mm and 483 ± 91 N, respectively) when compared to partially threaded parallel unicortical cancellous screw construct (111 ± 35 N/mm and 278 ± 49 N, respectively) in static load

[figure not shown]

Figure 1: Vertical shear medial malleolus fractures fixed with cancellous screws (left) and Acutrak screws (right) demonstrating the lack of hardware prominence after fixation as well as maintenance of reduction after off-set axial loading.

to failure testing of vertical medial malleolus fractures. Additionally, when the specimens were displaced to 6 mm and allowed to relax, the Acutrak headless compression screw constructs reduced to the pretesting fragment alignment while the parallel cancellous constructs remained displaced (see Figure 1).

HYPOTHESIS

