All continuous variables will be reported as the mean and errors are reported as standard deviation. All categorical variables will be reported as the subset number and percentage of the total. Comparisons will be performed with the appropriate statistical test when indicated. Statistical significance will be set at p less than 0.05 with an appropriate Bonferroni correction for multiple comparisons when indicated.

Budget

The vast majority of the budget will go toward an experienced fulltime clinical research coordinator, level II (CRCII, Table 2). This person is critical to our success. Appropriately, some funds will be devoted to insuring the proper training and certification for the CRCII involved in this project as well as supply adequate computing power and meet secure data storage needs. Some funds would be used by the principal investigator and co-investigators to offset local travel and travel to national and international meetings to present the findings of this interdisciplinary work, including the American Academy of Orthopaedic Surgeons (AAOS), the Orthopaedic Trauma Association (OTA), and the American Orthopaedic Foot and Ankle Society (AOFAS).

Table 2: General Budget

Expense			Effort	Cost
Personnel	Principal Investigator	[name]	10%	\$36,000/year
	Co-Investigator	[name]	3%	\$10,000/year
	Co-Investigator	[name]	3%	\$10,000/year
	Co-Investigator	[name]	3%	\$10,000/year
	Co-Investigator	[name]	3%	\$10,000/year
	Co-Investigator	[name]	3%	\$10,000/year
	CRCII	TBD: Stanford	100%	\$90,000/year

	CRCII	TBD: 3 rd center	75%	\$68,000/year
	CRCII	TBD: Kaiser	75%	\$68,000/year
Equipment	Computers			\$3,000/year
	Secure Storage			\$1,000/year
Training				\$5,000/year
Travel	Society Meetings			\$5,000/year
	Between Sites			\$5,000/year
				\$275,000/year

Acumed Study Summary	
Company	Stanford University
Title	Prospective, multi-center, randomized, controlled study evaluating the union rate, rate of medial malleolus hardware removal and clinical outcomes after medial malleolus fracture fixation with Acutrak headless compression screws
Short Title	Acutrak Fixation of Medial Malleolus Fractures
Protocol Number	
Treatment Device	Acutrak headless compression screws
Control Device(s)	Mini-fragment Plating, Antiglides Plating, Headed Unicortical Screws, Headed Bicortical Screws, Tension Band Wiring

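### Five control devices form one pooled arm, with no selection rule and no record of the intended device before allocation, so the estimate depends on the device mix and single-method comparisons would not be randomized

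*Combined protocol and SAP*

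**What the plan says.** The Hypothesis, repeated as the Study Purpose in the Acumed Study Summary, states that Acutrak screws give sufficient fixation and a favourable outcome "when compared to bicortical and unicortical screw fixation, tension band wiring, and mini-fragment or buttress plating". The Control Device(s) row of the summary lists "Mini-fragment Plating, Antiglides Plating, Headed Unicortical Screws, Headed Bicortical Screws, Tension Band Wiring".

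The Randomization section has two arms: "Patients will be randomized by sealed envelope to surgical fixation with traditional headed screws, plates, and wires or Acutrak headless compression screws". It continues: "At the time of randomization, the fracture pattern and severity, past medical history and medications, and demographic data will be documented". The intended control device is not in that list. Table 1 has an operative/device entry, which records what was implanted. No section says who selects the control device, by what rule, or when. No stratification and no analysis by device are described.

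The Specific Aims treat the comparator collectively. Aim 4, for example, seeks "superiority with respect to the hardware removal rate after Acutrak headless compression screw fixation when compared to other fixation methods for medial malleolus fractures". The Power Analysis section uses a single control rate: "the overall rate of hardware removal is 24% but if we can reduce half of the medial hardware removals the overall rate would be 14.5" (per cent).

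The background text before the Hypothesis reports bench stiffness for several of these constructs and adds: "Superior fixation requires extensive dissection and fixation known to result in prominent hardware and hardware related pain".

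**The concern.** The named comparators differ in ways that the protocol itself regards as important for its two main claims, which are equivalent union and fewer hardware removals. If stiffer constructs also bring more prominent hardware, device mix could act on the two claims in opposite directions. A control arm weighted towards plates would tend to raise the control removal rate. One weighted towards less stiff screws would make union equivalence easier to show. The pooled result would then depend partly on how often each device happened to be used.

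A reader of the Hypothesis will also want to know how Acutrak compares with plates, or with bicortical screws. The device is observed only in control patients and may well follow fracture pattern. Setting plated controls against all Acutrak patients would therefore compare different kinds of fracture. The variable that would make this a randomized comparison, the device intended before allocation, is not collected, and it cannot be reconstructed without bias once envelopes have been opened.

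**Working it through.** **1. The plan's own figure.** Inputs from Power Analysis and Statistics: 24% versus 14.5%, alpha 0.05, power 80%. Assumed: 1:1 allocation, since no ratio is stated.

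n per arm = [z_a·√(2·p̄·(1−p̄)) + z_b·√(p1(1−p1) + p2(1−p2))]² / (p1−p2)²

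- p̄ = (0.24 + 0.145)/2 = 0.1925, so √(2 × 0.1925 × 0.8075) = 0.5576.
- √(0.24 × 0.76 + 0.145 × 0.855) = 0.5535.
- One-sided: (1.645 × 0.5576 + 0.842 × 0.5535)² / 0.095² gives 212 per arm, 424 in total. This matches the plan.
- Two-sided: 270 per arm, 540 in total.

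The unstated sidedness is a separate matter. What counts here is that 424 is the size of one pooled two-arm comparison with one control rate.

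**2. Do the documents give reason to expect the controls to differ?** Bench stiffness in vertical fractures, from the background text:

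| Construct | Stiffness (N/mm) | Acutrak (244) relative to it |
|---|---|---|
| Unicortical screws | 111 | 244/111 = 2.20 |
| Bicortical screws | 279 | 244/279 = 0.87 |
| Antiglide plate | 463 | 244/463 = 0.53 |

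The controls span 463/111 = 4.2-fold, and Acutrak lies inside that range. No figures are given for tension band wiring or mini-fragment plating. Together with the stated link between stronger fixation and prominent hardware, this makes dependence on the mix plausible. It gives no clinical rates.

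**3. How far could the mix move the estimate?** No removal rate by device is given, so this is an illustration. Assume that some control devices have 18% removal and the rest 30% (24% at an equal split), with Acutrak fixed at 14.5%. With w the share of the 30% devices, the pooled control rate is 0.30w + 0.18(1−w).

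| w | Control rate | Difference | Power, 212 per arm, one-sided | Two-sided |
|---|---|---|---|---|
| 25% | 21% | 6.5 points | 54% | 42% |
| 50% | 24% | 9.5 points | 80% | 70% |
| 75% | 27% | 12.5 points | 94% | 89% |

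In general, the shift equals the gap between device rates times the change in share: here 12 points × 0.50 = 6 points. With no gap the shift is zero at any mix.

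**4. Could a single method be compared as planned?** If 212 controls split equally over five devices (assumed), each has 212/5 ≈ 42 patients. Against all 212 Acutrak patients at 24% versus 14.5%, power is 35% two-sided (46% one-sided) before any multiplicity correction. If one device takes 10% to 60% of controls, two-sided power is 25% to 59%. Besides being small, such a comparison would not be randomized.

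**The case against.** The strongest reply is that Acutrak against the usual mix of traditional fixation is a recognised pragmatic design and that the plan is coherent on it. All four aims, the secondary objectives, the sample size and the randomization use one collective comparator. The background also gives a reason for pooling: it treats thin soft-tissue cover over the medial malleolus as a problem that none of the existing methods solves, so headless against headed is the contrast of interest. This stands. Dependence on the mix limits what the estimate means; it does not bias the randomized comparison.

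Several stronger readings are tempting, and the documents do not support them:

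- **The trial claims a result against each of five methods.** The Hypothesis gives a list, but no aim or objective makes a separate claim for each method.
- **The surgeon picks the control device knowing the allocation.** The documents do not say who chooses or when. They only fail to require that the choice be made before the envelope is opened.
- **The matching Acutrak patients cannot be identified at all.** Fracture pattern and severity are recorded for everyone. To the extent that device follows pattern, analysis by pattern compares randomized groups. It is a partial proxy for intended device.
- **Union equivalence would be shown only against the weakest control.** Bench stiffness in vertical fractures is not evidence about union rates.
- **The size of the mix effect is known.** Every rate by device used here is assumed.

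**Conclusion.** The point holds as a limit on interpretation and as a missing baseline variable. The comparison of Acutrak with pooled traditional fixation is valid, but its estimate applies to whatever device mix occurs, and the plan neither controls that mix nor provides for analysing it. Conclusions about any one of the named methods would rest on non-randomized comparisons and, with an equal split, on about 42 controls each.

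How much the mix matters cannot be determined from the documents. The range of 6.5 to 12.5 points rests on the assumed 18% and 30% rates, on shares between 25% and 75%, and on an Acutrak rate fixed at 14.5%. A smaller gap between devices would shrink it in proportion. The change is worth making because it is cheap and the information is lost once allocation is known.

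**What to change.** In the Randomization section, require that for every patient, before the envelope is opened, the record states which listed control device would be used if the patient were allocated to control. Then, in the statistical section:

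- Adjust the main comparison for intended device class (screws, plate, tension band).
- Report the device mix, both intended and used.
- Report union, medial hardware removal and medial pain by intended class, with both arms in each class, as descriptive estimates with confidence intervals. Analyse by the declared device even if another was implanted.
- State the main conclusion as Acutrak versus traditional fixation in the mix used, and align the Hypothesis and Study Purpose with that, so that no separate claim against each named method is implied.

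The class results should not be made a test of agreement on which the main conclusion depends, because at this sample size they could differ by chance.

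The cost is one extra field on the eligibility worksheet and some added analysis text. The downsides are imprecise class estimates and some departures from the declared device at surgery. Nothing in the change affects which device a patient receives.

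### Allocation is by sealed envelope with no stated concealment safeguard, and nothing requires the fracture to be classified before the envelope is opened

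*Combined protocol and SAP*

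**What the plan says.** The Randomization section states: "Patients will be randomized by sealed envelope to surgical fixation with traditional headed screws, plates, and wires", with the headless screw as the other arm. The next sentence reads: "At the time of randomization, the fracture pattern and severity, past medical history and medications, and demographic data will be documented". The text available does not say how the sequence is generated, what the ratio is, or whether there is blocking or stratification. It does not say whether the envelopes are opaque or numbered, who holds them, or who opens them and when.

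Table 1 places the screening log, consent, eligibility worksheet, demographics, history, randomization and first radiographs in a single injury/office column. It states no order among them and has no row for fracture pattern.

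The study summary says: "Three Level I Trauma Centers will participate". The Randomization section names only two of these hospitals as recruiting. The summary lists the control devices as "Mini-fragment Plating, Antiglides Plating, Headed Unicortical Screws, Headed Bicortical Screws, Tension Band Wiring". No masking of surgeon, patient or assessor is described.

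The union definition ends with "a return to full weight bearing confirmed by the operating surgeon". The removal criteria begin: "Hardware may be removed if there is a surgical indication or patient/surgeon preference for removal".

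**The concern.** Envelopes conceal allocation only if nobody involved in enrolment can learn the next assignment, and if the patient is committed to the trial before the envelope is opened. The plan states neither condition. If the next arm were known or guessed, a patient could be approached, delayed or passed over according to how hard the fracture looked. If the fracture were classified after the arm was known, the baseline record could itself be coloured by the allocation.

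This trial has particular exposure. A headless screw is compared with plates, headed screws and wires, so the surgeon must know the arm and can see past assignments. The protocol's background also gives surgeons grounds for preferences in vertical fractures. It reports stiffness of 463 N/mm for antiglide plates, 279 for bicortical screws, 244 for the Acutrak construct and 111 for unicortical screws.

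Union is confirmed by the operating surgeon, and removal can follow from surgeon preference. Any imbalance created at enrolment would be mixed with unmasked outcome decisions, and the analysis could not readily separate the two. Steering on features that were never recorded cannot be reliably adjusted for later.

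**Working it through.** The core of the point is textual, so the relevant places are compared first. The arithmetic that follows is illustration only.

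**Text, side by side**

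- *Concealment.* The Randomization section says only that sealed envelopes are used. The rest of the document adds nothing on opacity, numbering, custody or opening.
- *Order of events.* Fracture data are tied to the moment of randomization. Table 1 gives one visit column for everything from screening to randomization. Neither place says whether classification comes before or after opening.
- *Surgeon's roles.* The arms are visibly different (control device list), the operating surgeon confirms union (union definition), and surgeon preference can lead to removal (removal criteria).

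**The plan's own sample size**, which supplies the standard error used below

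Inputs from the power section: 24% versus 14.5%, alpha 0.05, power 80%. A 1:1 ratio is assumed. Using pooled variance, no continuity correction and one-sided alpha:

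n per arm = [1.645 × √(2 × 0.1925 × 0.8075) + 0.842 × √(0.24 × 0.76 + 0.145 × 0.855)]² / 0.095² ≈ 212, or 424 in total.

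This matches the stated 424. The same formula with two-sided alpha gives 540. The plan does not state sidedness, so both are shown below.

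**Illustration of steering (every risk and share is an assumption)**

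Suppose there is no treatment effect. In a share s of places, a patient with 40% removal risk goes to control and one with 10% risk goes to Acutrak, in place of a typical 24% patient.

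- s = 5%: control 0.95 × 24 + 0.05 × 40 = 24.8%; Acutrak 0.95 × 24 + 0.05 × 10 = 23.3%; spurious difference 1.5 points.
- s = 10%: control 25.6%; Acutrak 22.6%; spurious difference 3.0 points, and 3.0/9.5 = 32% of the planned effect.

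SE = √(2 × 0.24 × 0.76 / 212) = 4.15 points, so the shift in z is 0.36 or 0.72.

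| s | Spurious difference | One-sided 5% rejection | Two-sided 5% rejection |
|---|---|---|---|
| 5% | 1.5 points | about 10% | about 6.5% |
| 10% | 3.0 points | about 18% | about 11% |

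Steering in the opposite direction reverses the sign. It would work against Acutrak and could hide a real benefit.

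**Illustration of guessing (block size assumed; none is stated)**

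If 1:1 blocks of known size were used and past assignments were visible, the best guess would be right 75.0% of the time with blocks of 2, 70.8% with 4, 68.3% with 6 and 66.6% with 8. The share of assignments known with certainty would be 50%, 33%, 25% and 20%. Under simple randomization guessing stays at 50%, and the remaining risk is early opening or reordering of envelopes.

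**The case against.** Sealed envelopes can conceal allocation if they are opaque, sequentially numbered, independently held and opened only after enrolment is irrevocable. Silence on these points does not show that they will be absent. Surgeons who cannot be masked are not in themselves a concealment failure, because they would know the implant under any system. Their knowledge of past assignments helps prediction only if allocation is restricted, and no blocking is stated.

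The plan also has partial safeguards. All eligible admissions are to be identified and asked for consent. A screening log would help to show whether eligible patients were set aside. Injury radiographs would let a reader blind to arm reclassify the fracture later, provided they precede fixation. No subgroup or covariate-adjusted analysis is specified, so harm to such analyses is hypothetical.

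All of this stands, and it limits the point. A reader might infer that envelopes sit with the surgical teams, that surgeons decide who is enrolled, that fractures are classified only after the arm is known, or that no trace of tampering could remain. The documents say none of these things. What survives is that no safeguard and no order of events is required. The log and radiographs help to detect or repair some problems afterwards, but they do not prevent foreknowledge.

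**Conclusion.** The point holds as a weakness in the specified method and merits a cheap improvement. The plan relies on sealed envelopes at several sites, states no concealment safeguard, and does not put classification of the fracture before opening. The operating surgeon necessarily knows the arm and influences two of the outcomes.

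The documents do not support the stronger reading that allocation would be foreseen or that the results would be biased beyond repair. They give no figure for the size of any bias. The 1.5 and 3.0 points, and the rejection rates of about 10% and 18% one-sided or 6.5% and 11% two-sided, rest entirely on assumed risks, an assumed share of steered places and an assumed direction. They show only that modest steering could matter next to a 9.5-point target. The absence of safeguards is judged on the text available, which lacks the protocol's opening part.

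**What to change.** In the Randomization section, replace the sealed-envelope method with central, computer-generated, time-stamped allocation, stratified by site, with variable block sizes that are not disclosed to the sites. Release the arm only after consent, eligibility, fracture pattern and severity, and the decision to fix the medial malleolus have been entered and locked. Name the same recruiting sites in this section as in the study summary, so that the strata are defined.

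The cost is a small set-up in an electronic data-capture system and a few protocol sentences. Coordinators, computers and secure storage are already in the budget. Emergency admissions need an out-of-hours backup, for example sequentially numbered opaque envelopes held independently of the surgical team and opened only after the baseline form is signed. The sample size does not change. If the sponsor prefers to keep envelopes throughout, writing those same conditions into the protocol would close most of the gap.
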